Over the last 2 decades, the model of Developmental Origin of Health and Disease (DOHaD) has extended from the spectrum of *in-utero* undernutrition to overnutrition. Through the follow-up study of mother-child pair from the "Hyperglycemia and Adverse Pregnancy Outcome" (HAPO) study participants, our group had demonstrated that maternal gestational diabetes mellitus (GDM) increased offspring's risk of DM, obesity and hypertension at 7 years of age, independent of various confounding factors, like maternal obesity and maternal DM status.⁷ Similar findings were reproduced by the multi-centre HAPO follow-up study funded by NIH and NIDDK, where our group shared our study design and was also one of the 10 study centres, when the children were 11-14 year of age.⁸ At the latest HAPO follow-up visit, 18% of 740 children assessed in the HK centre were diagnosed with prediabetes (based on their OGTT and HbA1c level) at their early teens.

The prevalence of maternal obesity and GDM are increasing worldwide. Up to 20-25% of pregnant mothers were affected by GDM in Hong Kong. A recent nation-wide study covering 31 provinces in mainland China discovered that 1.4% and 13% of women planning to get pregnant were diagnosed DM and prediabetes respectively, of whom, 8% were either overweight or obese.⁹ Taken together, the DOHaD model might help to explain the worldwide escalating prevalence of these metabolic diseases on top of our gene and lifestyle. The key concept of DOHaD is that the fetal and early infancy period is a window of plasticity, whereby the in utero programming can alter our gene expression.

Early studies in the 1980's on Pima Indian women had shown that the children and adolescent offspring of women with abnormal glucose tolerance during pregnancy were more obese and glucose intolerant, independent of their birth weight.^{10,11} It, therefore, suggested that maternal GDM was associated with long-term effects on obesity and glucose tolerance in the offspring. It has also been shown that offspring of type 1 DM mothers have an increased risk of developing DM in later life.¹² Study of amniotic fluid insulin by amniocentesis has demonstrated that excessive insulin secretion in utero was a strong predictor of impaired glucose tolerance (IGT) in the children

of DM mothers.¹³ This may explain the relationship between in-utero overstimulation of pancreatic cells and the subsequent reduction in insulin secretion in their later life.¹⁴

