- Augmentation index: Tonometer will be placed and gently compressed onto the radial artery with the subject's wrist in neutral position. A series of peripheral blood pressure waveforms are then captured by holding the tonometer for 10 seconds. Central aortic blood pressures and augmentation index will be computed by SphygmoCor® PVx after using the mathematical transfer function.
- Pulse wave velocity: Tonometer will be applied to carotid artery, radial artery and femoral artery in the same manner to obtain the peripheral blood pressure waveforms. The speed of BP wave which travels along the carotid, radial and femoral arteries are determined with reference to the ventricular contraction recorded from the ECG. The distances between the suprasternal notch (the notch at the top of the sternum) to the various tonometry points, namely carotid, radial femoral in order to compute the carotid-radial and carotid-femoral PWV. The acquisition of the data is non-invasive and the device has been approved by FDA.

Biochemical assay

Mothers will have fasting blood collected for the measurement of glucose, lipid profile, HbA1c, female hormonal profile (LH, FSH, estradiol, total testosterone, androstenedione, 17-OH and AMH) and renal function profile. The offspring will undergo a 75-gram OGTT with PG and insulin at 0, 30 and 120 minutes. Fasting blood will be taken from all offspring for lipid profile and renal function profile, whereas female hormonal profile will be assessed in female offspring only. HbA1c and lipid profile of the offspring will also be assessed by fasting blood. Blood for extraction of DNA will also be collected from offspring for genetic and epigenetic studies, including validation of established genetic risk scores for cardiometabolic traits.

Primary and secondary outcomes

The primary outcome is the rate of DM in the young adult offspring.

The secondary outcomes are their rate of impaired glucose regulation, obesity and adiposity, hypertension and various insulin indices (insulin sensitivity, pancreatic β -cell function, oral disposition indices).

iii) Statistical analysis

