Between-group comparison of outcomes between offspring of mothers with GDM and those of mothers with normal glucose tolerance will be made by using the Student's *t*-tests and the Chi-square/Fisher's exact tests, as appropriate. Group comparison of outcomes among offspring of mothers with inadequate, appropriate and excessive GWG will be made by using ANOVA test. Linear and logistic regression analyses with the adjustments for potential confounders will be used to assess the associations for continuous and binary outcome variables, respectively. Any sex difference in the associations will be performed in subgroup analysis. Data will be presented as beta with standard error for continuous outcomes, and odds ratios (ORs) with 95% confidence intervals for binary outcomes.

The data from FFQ will be analysed by using the nutrition analysis software Food Processor Nutrition analysis and Fitness software version 8.0 (ESHA Research, Salem, USA) with specific focus on local foods consumption from Mainland and Hong Kong. Dietary patterns of the studied population will be generated by principal component analysis.

iv) Sample size and power calculation

We estimate the sample size and calculate the power using the objective 1.

Assuming an 50% response rate of the eligible subjects, around 900 mother-child pairs will be recruited. Our previous findings detected an adjusted OR of 1.8-2.0 in children's abnormal glucose regulation with per SD rise in maternal fasting, 1-hour and 2-hour PG at OGTT during pregnancy. We estimate the overall prevalence rate of type 2 DM as 2% in this young age group, the sample size will be able to detect a similar odds ratio of 1.8 per SD rise in glycaemic levels, at 80% power and a significance level of 0.05 by using logistic regression analysis.³⁶

v) Duration of study

We estimate two and half year to complete the recall of all the HAPO mother-child pairs Another 6 months will be required for the data analysis.

This protocol is in compliance with the Declaration of Helsinki.

Reference

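### Sex differences in the associations are left to subgroup analysis, with no test of the difference between the sexes

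*Protocol*

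**What the plan says.** The protocol, section iii) Statistical analysis, gives one sentence to the question: "Any sex difference in the associations will be performed in subgroup analysis".

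The sentence before it sets the models: "Linear and logistic regression analyses with the adjustments for potential confounders will be used to assess the associations for continuous and binary outcome variables, respectively". The sentence after it sets the reporting: "Data will be presented as beta with standard error for continuous outcomes, and odds ratios (ORs) with 95% confidence intervals for binary outcomes".

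The same section names t-tests, chi-square or Fisher tests and ANOVA for its other comparisons. Neither there nor elsewhere does the protocol name an exposure-by-sex term, a heterogeneity test or a comparison of sex-specific coefficients.

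The primary outcome is diabetes in the offspring: "The primary outcome is the rate of DM in the young adult offspring". Sex difference appears in neither of the two objectives and is not listed among the outcomes.

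**The concern.** Whether an association differs by sex is a question about a contrast. Fitting the model in each sex gives two estimates, each tested against no association. It does not give a test of one against the other. A significant result in one sex and a non-significant result in the other is not evidence of a difference, especially when each half of the cohort has few events.

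The protocol does not say how the two sets of results will be compared. If they are read by significance within each sex, a sex-specific effect could be reported where the true effect is the same in both. The sentence covers every exposure and outcome, so the comparison may be made many times.

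**Working it through.** **Inputs from the protocol, section iv).** "around 900 mother-child pairs will be recruited"; "We estimate the overall prevalence rate of type 2 DM as 2% in this young age group"; "odds ratio of 1.8 per SD rise in glycaemic levels, at 80% power and a significance level of 0.05 by using logistic regression analysis". Expected diabetes cases: 900 × 0.02 = 18. From the background: "18% of 740 children assessed in the HK centre were diagnosed with prediabetes", used below as an example of a commoner outcome.

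**Assumptions not in the protocol.** Equal numbers of each sex (450 each, about 9 cases each), equal prevalence in both sexes, a standard-normal exposure, no covariates, two-sided 0.05 Wald tests.

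**The plan's own figure.** No figure is given for the sex comparison. For the whole cohort, n = (z_α + z_power)² / [p(1−p)(ln OR)²], with p(1−p) = 0.0196 and ln 1.8 = 0.588:
- one-sided 0.05: about 913, which matches the stated 900;
- two-sided 0.05: about 1,160, with 69% power at 900.

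The protocol does not state the sidedness. That is a separate matter and this point does not rest on it.

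**Reading by significance within each sex, diabetes, OR 1.8 in both.**
- Power within one sex = Φ(√(450 × 0.0196) × 0.588 − 1.96) = 0.415.
- The sexes are independent samples, so P(exactly one significant) = 2 × 0.415 × 0.585 = 48.6%.
- Simulation (10,000 cohorts of 900): exactly one sex 48.3%, both 15.7%, neither 36.0%.
- The test (b_m − b_f)/√(SE_m² + SE_f²) rejects in 4.8% of the same cohorts.
- With a 45:55 or 40:60 split, exactly one sex is significant in 48.4% or 48.8%.

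**Dependence on power.** The quantity 2π(1−π), where π is within-sex power, peaks at 50% when π = 0.5 and is at least 32% for any π between 0.2 and 0.8.

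| Setting | Exactly one sex significant, formula | Simulated |
|---|---|---|
| 2%, OR 1.8 | 48.6% | 48.3% |
| 2%, no association | 2 × 0.05 × 0.95 = 9.5% | 9.0% |
| 18%, OR 1.8 | 0.5% | 0.7% |
| 18%, OR 1.3 (assumed) | 49% | 48.6% |

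**What an interaction test can detect for diabetes.**
- SE of the log ratio of ORs = √(2/(450 × 0.0196)) = 0.476.
- Ratio of ORs for 80% power = exp(2.802 × 0.476) = 3.8. Simulated power at that ratio is 74%, so the formula is slightly optimistic.
- Power at a ratio of 2: Φ(0.693/0.476 − 1.96) = 31% by formula, 27% simulated.

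**The case against.** The strongest objection is that this is detail for the SAP, which may exist and is not shown. The term subgroup analysis is sometimes used loosely to include an interaction test, and the sentence does name the difference as its object. The protocol nowhere says that within-sex P values will be compared. It plans estimates with standard errors or confidence intervals, from which a valid test can be computed. The 48% is therefore the error rate of a reading that the protocol does not describe.

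The size is also conditional. The protocol's OR of 1.8–2.0 was observed for abnormal glucose regulation in children, and at 18% prevalence with OR 1.8 the misreading is rare. The 49% at that prevalence needs an OR of 1.3 that the protocol does not give. The planned models are adjusted, continuous outcomes are not quantified here, and an interaction test on about 18 cases will detect little.

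Most of this stands as a limit on the size of the point. It does not remove it. The protocol does more than leave the method blank: it states the question and names a method which, taken literally, does not answer it. A SAP that followed the sentence as written would carry the gap forward. If an interaction test is what is meant, one clause confirms it. Low power for that test is a reason to say so in advance and does not justify relying on separate estimates.

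**Conclusion.** The point holds. The named method does not test the stated question, and no test that would do so is specified. If subgroups are read by within-sex significance, the diabetes outcome would show an effect in exactly one sex in about 48% of cohorts when the true OR is 1.8 in both, against about 5% for a test of the difference. That figure rests on the protocol's 900 pairs, 2% prevalence and OR 1.8, and on an assumed near-equal split, equal prevalence in both sexes and no covariates. The risk is under 1% where within-sex power is very high, and about 9% where there is no association.

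The consequence is confined to a secondary, exploratory analysis; the primary whole-cohort association is unaffected. The change should be made because it prevents an avoidable false claim at almost no cost.

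**What to change.** Replace the sentence in section iii) with:

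> Sex differences in the associations will be tested by an exposure × sex term in the adjusted linear or logistic model for the whole cohort (or an equivalent test of the difference between sex-specific coefficients). The interaction estimate with its 95% CI and P value will be reported, and sex-specific estimates will be descriptive.

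Add that this analysis is exploratory and that power for interaction on diabetes is low, so a non-significant interaction is not evidence of equal effects.

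The cost is a short text change and one model term, or one comparison of coefficients already planned for reporting. No new data or participants are needed.

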The available data would have great potential to explore the effect of in utero vitamin D status and long-term cardiometabolic risk at early teens and young adulthood. Our preliminary finding is consistent with the previous report showing vitamin D insufficiency in adult was associated with increase arterial stiffness and endothelial dysfunction.²⁹ Experimental studies did suggest that vitamin D modulated the endothelial cell function by reducing the endothelium-dependent contraction and regulating the calcium influx.^{30,31} Vitamin D may affect the vascular wall through the renin-angiotensin-aldosterone axis and takes part in the lymphocyte and monocyte/macrophage differentiation and secretion of inflammatory cytokines which determines the monocyte infiltration and cholesterol retention in the vascular wall.^{32,33}

Our research team has been investigating the effect of maternal hyperglycaemia, under- and overnutrition on the children's long-term cardiometabolic risk in the HAPO study cohort over the last 10 years. We have the most comprehensive data among all HAPO study centres, including offspring's BP, BMI, skinfold thickness, 5 point OGTT with insulin levels to explore their trajectories, plus the pre-pregnant BMI and information on GWG

Now that the HAPO cohort children are reaching young adulthood. We have archived important antenatal, childhood data, maternal serum and cord blood serum, and cord blood DNA material to determine these associations and their possible mechanism. Epigenome-wide association study (EWAS) was already performed to identify differentially methylated loci and regions in cord blood DNA in offspring which was supported by previous GRF.

Since the mothers have not been subjected to antenatal treatment on the various degree of maternal hyperglycaemia in pregnancy, this is a unique cohort that enables us to determine the effect of various degree of maternal hyperglycaemia below the level of overt DM, on children's cardiometabolic risk in Chinese population.

Our research team has successfully followed up more than 70% children from the original HAPO cohort, even though we only started to re-contact them a few years after the completion of the HAPO study; we are keeping them in contact for future assessment. Among those we have been in

touch with, we expect a higher response rate among those who have attended the last two follow-up studies and estimate a response rate of 80% in the proposed study.

Objectives

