1. To assess maternal glycaemic levels, gestational weight gain and pre-pregnancy BMI in the prediction of offspring's risk of DM, hypertension and obesity at 18-20 years of age.
2. To determine the trajectory of insulin resistance and pancreatic beta cell functions at 7 years and 11-14 years of age in association with corresponding BMI to the development of young-onset type 2 DM at 18-20 years of age.

Research plan and methodology

i) Subjects

Our unit is one of the centres contributing to the International multicentre HAPO study. We recruited 1760 Chinese pregnant women between 2000 and 2005. The HAPO study investigated whether any adverse outcome was associated with mild degree of GDM. All mothers underwent a 75-gram OGTT at 24-32 weeks gestation, but clinicians were blinded to the results as long as the fasting PG was ≤ 5.8 mmol/L & 2-hour PG ≤ 11.1 mmol/L. The maternal serum C-peptide and HbA1c, cord serum C-peptide and early neonatal PG, pregnancy outcome and the neonatal anthropometric parameters are available for future study. This is so far the largest cohort in a Chinese population who has been investigated for glycaemia during pregnancy, but with OGTT results remained undisclosed to subjects and clinicians. This unique cohort can allow us to study the effect of in-utero hyperglycemia on the cardiometabolic risks at childhood, adolescence and adulthood.

Eligible subjects are all mother-child pairs participating in the original HAPO study. Children born preterm before 37 weeks of gestation, non-Chinese and whose mother's OGTT result were unblinded during pregnancy will be excluded. The family (the child and the mother) will be invited for a third follow-up assessment.

ii) Data collection

Questionnaire, anthropometry and BP measurement

Detail clinical information on maternal characteristics during pregnancy (mothers' smoking history, alcohol use and smoking habit, pregnancy complications, mode of delivery and gestational age at delivery), children's characteristics at birth, at 7 and 11-14 years of age were available in our dataset from the original HAPO study and the two follow-up studies.^{7,8}

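### The stated 80% power for an odds ratio of 1.8 holds at about 900 pairs only with an undeclared one-sided test; two-sided it is about 68-69%, and half the cohort is at most 880 pairs

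*Protocol*

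**What the plan says.** The primary outcome is the rate of diabetes in the young adult offspring (protocol, Primary and secondary outcomes). The sample size is argued in section iv) Sample size and power calculation, under objective 1:

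- Recruitment: "Assuming an 50% response rate of the eligible subjects, around 900 mother-child pairs will be recruited".
- Event rate: "We estimate the overall prevalence rate of type 2 DM as 2% in this young age group".
- Effect and power: "the sample size will be able to detect a similar odds ratio of 1.8 per SD rise in glycaemic levels, at 80% power", at a significance level of 0.05 with logistic regression. The sidedness of the test is not given.

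Three other places bear on this:

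- Section i) Subjects gives the base: "We recruited 1760 Chinese pregnant women between 2000 and 2005". It then narrows it: "Children born preterm before 37 weeks of gestation, non-Chinese and whose mother's OGTT result were unblinded during pregnancy will be excluded". No counts are given for the exclusions.
- Section iii) Statistical analysis will report "odds ratios (ORs) with 95% confidence intervals for binary outcomes", from regressions adjusted for potential confounders.
- The paragraph before the Objectives gives a second response rate, 80%, introduced by "we expect a higher response rate among those who have attended the last two follow-up studies".

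**The concern.** Two figures in section iv do not fit the rest of the protocol.

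First, 900 pairs at 50% response needs 1,800 eligible pairs, which is more than the whole cohort before anyone is excluded. Second, 2% of 900 is only 18 diabetes cases, which is thin for 80% power at an odds ratio of 1.8 per SD.

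If the power is overstated, a null result on the primary outcome would be read against an 80% chance of detection that the study never had. Section iv is the only place where the protocol justifies its size.

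**Working it through.** **Inputs (all from the protocol).** Cohort 1,760 (section i). Response 50%, N about 900, prevalence p = 0.02, odds ratio 1.8 per SD, significance level 0.05, power 80% (section iv).

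**Step 1: number of pairs.** 0.5 × 1,760 = 880, and 900 / 0.5 = 1,800 > 1,760. So 880 is the most that a 50% response can give, before exclusions.

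**Step 2: formula.** For one continuous, roughly normal exposure in logistic regression (Hsieh):

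power = Φ( √[N · p(1−p) · (ln OR)²] − z )

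Here p(1−p) = 0.0196 and (ln 1.8)² = 0.5878² = 0.3455.

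**Step 3: reproduce the stated 80%.** One-sided 0.05, z = 1.645:

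- N = 900: √(900 × 0.0196 × 0.3455) = 2.469, and Φ(2.469 − 1.645) = 79.5%.
- N needed: (1.645 + 0.8416)² / (0.0196 × 0.3455) = 913.
- The older Whittemore/Hsieh formula gives N = 900 and power 80.0%.

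The stated figure therefore matches a one-sided test almost exactly.

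**Step 4: two-sided 0.05, z = 1.96.**

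| Pairs | Expected cases | Power | Odds ratio detectable with 80% power |
|---|---|---|---|
| 900 | 18.0 | 69.5% | 1.95 |
| 880 | 17.6 | 68.5% | 1.96 |

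The detectable odds ratio is exp(2.8016 / √(0.0196 N)). N for 80% power is (1.96 + 0.8416)² / (0.0196 × 0.3455) = 1,159, or about 1,160 pairs. That is 1,159 / 1,760 = 66% of the entire cohort.

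**Step 5: other methods, two-sided.**

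| Method | Power at 880 | Power at 900 | N for 80% |
|---|---|---|---|
| Whittemore/Hsieh | 68.1% | 69.1% | 1,150 |
| Demidenko (two variants) | 67.4-68.3% | 68.3-69.2% | 1,168-1,189 |
| Simulation (4,000 and 5,000 runs; Wald and likelihood ratio) | about 67% | 67-68% | above 1,159 (78% there) |

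If 2% is read as the risk at mean glucose, although the protocol calls it overall, 900 pairs give 75-76% by the Demidenko formula and 73-74% by simulation. No two-sided version reaches 80%.

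**Step 6: sensitivity to what the protocol does not give (assumptions).**

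- Exclusions of 5%: 0.5 × 1,672 = 836 pairs, 17 cases, power 66%, detectable odds ratio 2.00.
- Exclusions of 20%: 0.5 × 1,408 = 704 pairs, 14 cases, power 59%, detectable odds ratio 2.13.
- Confounders explaining 10% of the exposure variance: Φ(√(6.094 × 0.9) − 1.96) = 64.9% at 900 pairs.

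**The case against.** The strongest reply is that the 80% is not a slip: it is what a one-sided 0.05 calculation returns, and section iv never says two-sided. That explains the figure but does not justify it. No one-sided test is declared or argued for, objective 1 has no direction, and 95% confidence intervals correspond to a two-sided 0.05 test.

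Other points carry weight:

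- The gap between 880 and around 900 is 2% and costs about one point of power. Taken alone it is rounding; the sidedness drives the shortfall.
- The cohort is described as Chinese, so the non-Chinese exclusion may remove few or none. The preterm and unblinded exclusions still apply. The 20% end of the exclusion range has no support in the protocol and only shows direction.
- Section iv cites earlier adjusted odds ratios of 1.8 to 2.0. At 2.0, two-sided power at 900 is 82.9% by formula. The shortfall therefore concerns the lower end, but that is the value to which the protocol attaches its 80%.
- The closed formulas are slightly optimistic with so few events. Simulated power at 900 pairs and an odds ratio of 1.95 is about 77%, so the replacement figures should be read as approximate.
- The 80% response seems to apply to families already in touch, so it is an unclear denominator rather than a proven contradiction. Taking the more than 70% followed up as 70%, 1,760 × 0.7 × 0.8 = 986 pairs, with 73% two-sided power. Only 80% of the whole cohort (1,408 pairs, 87%) would reach the target.

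**Conclusion.** The concern holds. With the protocol's own prevalence, effect size and significance level, 880 to 900 pairs give about 68-69% two-sided power by formula and about 67-68% by simulation, against the stated 80%. At 900 pairs the chance of missing an odds ratio of 1.8 is about 31%, not 20%. Eighty per cent needs about 1,160 pairs or somewhat more.

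On the stated 50% response, 880 is the ceiling before exclusions. These results assume a two-sided test, a roughly normal exposure, 2% as the overall prevalence and no confounder adjustment. Adjustment and exclusions can lower power further, by amounts the protocol does not allow one to fix.

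**What to change.** Revise section iv as follows:

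1. Take the number of eligible pairs, after the exclusions in section i, from the existing database.
2. Apply one response rate, state its denominator, and use it consistently in section iv and in the paragraph before the Objectives.
3. State the sidedness of the test. Two-sided fits the planned confidence intervals.
4. Restate N, the expected number of diabetes cases, and either the power at an odds ratio of 1.8 or the odds ratio detectable with 80% power. By formula, two-sided and unadjusted, the latter is about 1.95 at 900 pairs and 1.96 at 880. A simulation at the final N would be safer with so few events.
5. Say what confounder adjustment is assumed to cost.

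This changes text only and needs no new data. The price is a less favourable N and power statement.

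### The 80% power claim at an odds ratio of 1.8 holds for a one-sided 0.05 test; at two-sided 0.05, which the planned 95% intervals imply, power is about 68–70% for a normal exposure.

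*Protocol*

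**What the plan says.** Section iv (Sample size and power calculation) bases the calculation on objective 1. It is the only power statement for the primary outcome, the rate of diabetes in the young adult offspring.

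- Size: "Assuming an 50% response rate of the eligible subjects, around 900 mother-child pairs will be recruited".
- Event rate: "We estimate the overall prevalence rate of type 2 DM as 2% in this young age group".
- Effect: "Our previous findings detected an adjusted OR of 1.8-2.0" per SD of maternal glucose, for abnormal glucose regulation in childhood.
- Claim: "the sample size will be able to detect a similar odds ratio of 1.8 per SD rise in glycaemic levels, at 80% power".
- Test: described only as "at 80% power and a significance level of 0.05 by using logistic regression analysis".

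Section iii (Statistical analysis) says that "Linear and logistic regression analyses with the adjustments for potential confounders will be used", and that results will be given as "odds ratios (ORs) with 95% confidence intervals for binary outcomes".

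The protocol does not say whether the test is one- or two-sided. It does not describe the distribution of maternal glucose, and the power sentence makes no stated allowance for covariate adjustment. A power-analysis software paper is cited, but not the settings used.

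**The concern.** A 95% confidence interval excludes an odds ratio of 1 exactly when a two-sided test at 0.05 rejects. A reader will therefore take the unqualified 0.05 as two-sided. With only about 18 expected cases there is little room in the calculation, and the choice of side moves power by about 10 points.

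At stake is how a null result is read. The protocol implies a 20% chance of missing an odds ratio of 1.8. If the test is two-sided and the exposure roughly normal, that chance is about 30%, before any loss from confounder adjustment.

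**Working it through.** **Inputs from section iv.** n = 900; p = 0.02, so 900 × 0.02 = 18 cases; OR = 1.8 per SD, so ln 1.8 = 0.5878 and its square is 0.3455; α = 0.05; power 80%. **Assumption added here:** a normally distributed exposure, no covariates.

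**1. Reproducing the stated figure, one-sided.** The Hsieh formula is n = (z_α + z_power)² / [p(1 − p)(ln OR)²].

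- n = (1.645 + 0.842)² / (0.0196 × 0.3455) = 913
- Power at 900 = Φ(√(900 × 0.0196 × 0.3455) − 1.645) = Φ(2.469 − 1.645) = 79.5%

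The Whittemore formula gives n = 900 for 80%. The protocol's numbers therefore reproduce one-sided.

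**2. The same inputs, two-sided.**

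- n = (1.960 + 0.842)² / (0.0196 × 0.3455) = about 1,159
- Power at 900 = Φ(2.469 − 1.960) = 69.5%

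**3. Other methods.** The Wald calculation integrates the logistic information over a normal exposure, with the intercept set so that overall prevalence is 2%. The simulation used 10,000 data sets.

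| Method (n = 900, OR 1.8, overall 2%) | One-sided | Two-sided | n for 80%, two-sided |
|---|---|---|---|
| Hsieh | 79.5% | 69.5% | 1,159 |
| Whittemore | 80.0% | 69.1% | 1,149 |
| Wald, numerical integration | 78.6% | 68.3% | 1,189 |
| Simulation (Wald / likelihood ratio) | – | 68.5% / 68.9% | – |

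**4. What 900 pairs can detect, two-sided.**

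- Detectable OR at 80% power: exp(2.802 / √(900 × 0.0196)) = exp(0.667) = 1.95 (Hsieh); 1.97 (Wald).
- Power at OR 1.9: 76.9% (Hsieh), 75.6% (Wald).
- Power at OR 2.0: 82.9% (Hsieh), 81.5% (Wald), 80.9% (simulation, Wald test).
- Prevalence needed for 80% at OR 1.8: 2.59% (Hsieh) to 2.68% (Wald), or 23–24 cases instead of 18.

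**5. Other readings, two-sided at OR 1.8.**

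- *2% taken as the risk at mean glucose.* Overall prevalence becomes about 2.35% and power 74.8% (Wald). The text calls the 2% an overall prevalence.
- *Right-skewed exposure.* The values below are for an assumed standardised gamma exposure, by simulation (Wald / likelihood ratio).

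| Skewness (assumed) | Overall 2% | 2% at mean glucose |
|---|---|---|
| 0.3 | 72.2% / 71.3% | 79.1% / 78.2% |
| 0.6 | 76.9% / 75.2% | 83.0% / 81.7% |
| 0.8 | 79.2% / 76.9% | – |
| 1.0 | 81.8% / 79.4% | – |

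- *Literal 50% response.* 0.5 × 1,760 = 880 pairs: 68.5% (Hsieh), 67.4% (Wald).
- *The 80% response rate in the background, which the power sentence does not use.* Applied to the roughly 70% already followed, 0.8 × 0.7 × 1,760 = 986 pairs: 73.4% / 72.3%. Applied to the whole cohort, 0.8 × 1,760 = 1,408 pairs: 87.0% / 86.2%.
- *Covariate adjustment.* If glucose shares an assumed R² of 0.05 to 0.20 with the adjustment covariates, two-sided Hsieh power at 900 falls to 67% to 60%.

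**The case against.** **The 80% is not shown to be a slip in arithmetic.** It reproduces under a one-sided test, which the text does not exclude. That stands: the defect is an unstated basis that does not match the planned intervals. A one-sided 0.05 test cannot be read off a 95% interval, so leaving the side open does not settle the matter.

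**Normality is an added assumption, and skewness could account for the figure.** This stands in part. The large-sample Wald formula for a gamma exposure reaches two-sided 80% at a skewness of about 0.5 with overall prevalence 2%. A planner using that formula could have arrived at 80% without a one-sided test, so the origin of the figure cannot be established. Simulation at 18 expected cases is less favourable and puts the threshold at about 0.8–1.0. Excluding mothers whose glucose results were unblinded trims the upper tail, but by how much is unknown, and no 1-hour limit is given. The protocol states no skewness, so it cannot rely on one.

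**The practical effect is small.** This also stands. All eligible pairs in a closed cohort are invited, so the number studied depends on response, and the 2% is itself an estimate. An odds ratio of 2.0 lies within the cited range and is adequately powered. This limits the remedy, but the claim made is 80% at 1.8.

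**Conclusion.** The point holds. With about 900 pairs, 2% overall prevalence and an odds ratio of 1.8 per SD, unadjusted power at two-sided 0.05 is about 68–70% for a normal exposure, 10–12 points below the stated 80%. The type II error is then about 30% instead of 20%.

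The conclusion rests on two conditions: a two-sided test, which the planned 95% intervals imply, and an approximately normal exposure, which the protocol neither states nor rules out. What changes is the effect the study can claim to detect with 80% power: about 1.95–1.97 instead of 1.8. A later choice of side in an analysis plan would not repair the printed sentence. Two-sided leaves the 80% unsupported under a normal exposure; one-sided leaves the intervals mismatched.

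**What to change.** Declare the test two-sided and restate the last sentence of section iv along these lines:

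> With about 900 pairs and an overall prevalence of 2% (about 18 cases), at two-sided alpha 0.05 and assuming an approximately normal exposure, unadjusted power is about 70% for an odds ratio of 1.8 per SD. Power of 80% is reached at an odds ratio of about 1.95–2.0. Correlation between maternal glucose and the adjustment covariates is not allowed for and would lower these figures.

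If a one-sided test was intended, the section must say so, and the interval reporting in section iii must be reconciled with it. Optionally, check the normality assumption against data already held, since section i records that "All mothers underwent a 75-gram OGTT at 24-32 weeks gestation".

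The cost is one sentence and a less favourable stated figure. Recruitment, endpoint and analysis stay as they are.
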